- After completion of the first two follow -up visits (FU 1 at day 30 days \pm 1 week and FU 2 at 84 days \pm 1 week from FU1),

See the details in [Table 5.1-3](#)

- Subjects who discontinue treatment for reasons other than distant recurrence will continue to have surveillance assessments (until distant recurrence) every 12 weeks \pm 1 week during the first year after randomization, every 12 weeks \pm 2 week during the second year, after that follow local standard in the range of 6-12 months between year 3 and year 5 with the last assessment at year 5. See the details in [Table 5.1-3](#)
- All adverse events will be documented for a minimum of 100 days after the last dose of study drug Subjects will be followed for drug-related toxicities until these toxicities resolve, return to baseline or are deemed irreversible. See the details in [Table 5.1-3](#)
- The Outcomes Research Assessments, Health Care Resource Utilization data collection, and biomarker sampling will continue as detailed in [Table 5.1-3](#)

[REDACTED]

[REDACTED]

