- medical/surgical admission other than to remedy ill health and planned prior to entry into the study. Appropriate documentation is required in these cases
- admission encountered for another life circumstance that carries no bearing on health status and requires no medical/surgical intervention (eg, lack of housing, economic inadequacy, caregiver respite, family circumstances, administrative reason).
- Admission for administration of anticancer therapy in the absence of any other SAEs

6.1.1 *Serious Adverse Event Collection and Reporting*

Sections 5.6.1-1 and 5.6.1-2 in the Investigator Brochure (IB) represent the Reference Safety Information to determine expectedness of serious adverse events for expedited reporting. Following the subject's written consent to participate in the study, all SAEs, whether related or not related to study drug, must be collected, including those thought to be associated with protocol-specified procedures. All SAEs must be collected that occur during the screening period and within 100 days of discontinuation of dosing. If applicable, SAEs must be collected that relate to any later protocol-specified procedure (eg, a follow-up skin biopsy).

The investigator must report any SAE that occurs after these time periods and that is believed to be related to study drug or protocol-specified procedure.

An SAE report must be completed for any event where doubt exists regarding its seriousness.

If the investigator believes that an SAE is not related to study drug, but is potentially related to the conditions of the study (such as withdrawal of previous therapy or a complication of a study procedure), the relationship must be specified in the narrative section of the SAE Report Form.

SAEs, whether related or not related to study drug, and pregnancies must be reported to Sponsor or designee within 24 hours of awareness of the event. SAEs must be recorded on the SAE Report Form; pregnancies on a Pregnancy Surveillance Form (electronic or paper forms). The preferred method for SAE data reporting collection is through the eCRF. The paper SAE/pregnancy surveillance forms are only intended as a back-up option when the eCRF system is not functioning. In this case, the paper forms are to be transmitted via email or confirmed facsimile (fax) transmission to:

SAE Email Address: Refer to Contact Information list.

SAE Facsimile Number: Refer to Contact Information list.

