6.2.1 Nonserious Adverse Event Collection and Reporting

The collection of nonserious AE information should begin at initiation of study drug. Nonserious AE information should also be collected from the start of a placebo lead-in period or other observational period intended to establish a baseline status for the subjects.

All nonserious adverse events (not only those deemed to be treatment-related) should be collected continuously during the treatment period and for a minimum of 100 days following discontinuation of study treatment. Nonserious AEs should be followed to resolution or stabilization, or reported as SAEs if they become serious (see [Section 6.1.1](#)). Follow-up is also required for nonserious AEs that cause interruption or discontinuation of study drug and for those present at the end of study treatment as appropriate. All identified nonserious AEs must be recorded and described on the nonserious AE page of the CRF (paper or electronic).

Completion of supplemental CRFs may be requested for AEs and/or laboratory abnormalities that are reported/identified during the course of the study.

Every adverse event must be assessed by the investigator with regard to whether it is considered immune-mediated. Immune-mediated adverse events (IMAEs) are AEs consistent with an immune-mediated mechanism or immune-mediated component for which non-inflammatory etiologies (eg, infection or tumor progression) have been ruled out. IMAEs can include events with an alternate etiology that were exacerbated by the induction of autoimmunity. Information supporting the assessment will be collected on the subject's case report form.

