 - On-treatment AEs will be defined as AEs with an onset date and time on or after the date and time of the first dose of study treatment (or with an onset date on or after the day of first dose of study treatment if time is not collected or is missing). For subjects who are off study treatment, AEs will be included if event occurred within a safety window of 30 days (or 100 days depending on the analysis) after the last dose of study treatment. No “subtracting rule” will be applied when an AE occurs both pre-treatment and post-treatment with the same preferred term and grade.
 - On-treatment evaluations (laboratory tests, and vital signs) will be defined as evaluations taken after the day (and time, if collected and not missing) of first dose of study treatment. For subjects who are off study treatment, evaluations should be within a safety window of 30 days (or 100 days depending on the analysis) after the last dose of study treatment.

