7.6 Safety

7.6.1 Deaths

Deaths will be summarized by treatment group:

- All deaths, reasons for death.
- Deaths within 30 days of last dose received, reasons for death.
- Deaths within 100 days of last dose received, reasons for death.

A by-subject listing of deaths will be provided for the all enrolled subjects population.

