7.6.2 Serious Adverse Events

Serious adverse events will be summarized by treatment group:

- Overall summary of SAEs by worst CTC grade (any grade, grade 3-4, grade 5) presented by SOC/PT.
- Overall summary of drug-related SAEs by worst CTC grade (any grade, grade 3-4, grade 5) presented by SOC/PT.

All analyses will be conducted using the 30-day safety window.

A by-subject SAE listing will be provided for the “enrolled subjects” population.

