7.6.5 Adverse Events

Adverse events will be summarized by treatment group.

The following analyses will be conducted using the 30 days safety window only:

- Overall summary of any AEs by worst CTC grade (1, 2, 3, 4, 5, not reported, total) presented by SOC/PT.
- Overall summary of any AEs presented by worst CTC grade (any grade, grade 3-4, grade 5) by SOC/PT. This table will be restricted to events with an incidence greater or equal to 5% in any treatment group.
- Overall summary of any non-serious AEs presented by SOC/PT. This table will be restricted to events with an incidence greater or equal to 5% in any treatment group.
- Overall summary of any AEs that required immune modulating medication by worst CTC grade (any grade, grade 3-4, grade 5) presented by SOC/PT.
- Overall summary of drug-related AEs by worst CTC grade (1, 2, 3, 4, 5, not reported, total) presented by SOC/PT.

The following analyses will be conducted using the 30 days safety window and repeated using the 100 days safety window:

- Overall summary of drug-related AEs by worst CTC grade (any grade, grade 3-4, grade 5) presented by SOC/PT.

A by-subject AE listing will be provided. A by-subject listing of any AE requiring immune modulating medications will also be provided.

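### SAE tables and overall all-cause AE tables stop 30 days after last dose although the protocol collects both to 100 days, so SAEs as a category have no specified comparison by arm for days 31–100

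*SAP*

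**What the plan says.** **Collection.** For SAEs, Protocol 6.1.1 states "All SAEs must be collected that occur during the screening period and within 100 days of discontinuation of dosing", and it applies this to related and unrelated events alike. For nonserious AEs, Protocol 6.2.1 says they "should be collected continuously during the treatment period and for a minimum of 100 days following discontinuation of study treatment", again whatever the attribution. Protocol 3.1 repeats the rule: "All adverse events will be documented for a minimum of 100 days after the last dose of study drug".

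**Analysis.** SAP 6.1 counts post-dose AEs that occur "within a safety window of 30 days (or 100 days depending on the analysis) after the last dose of study treatment", which leaves the choice to each analysis.

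- SAP 7.6.2 (all-cause SAEs and drug-related SAEs by worst grade): "All analyses will be conducted using the 30-day safety window". A by-subject SAE listing is added.
- SAP 7.6.5, first group (including the all-cause AE tables): "The following analyses will be conducted using the 30 days safety window only".
- SAP 7.6.5, second group (drug-related AEs by worst grade): "The following analyses will be conducted using the 30 days safety window and repeated using the 100 days safety window".
- SAP 7.6.1 includes among its summaries by treatment group: "Deaths within 100 days of last dose received, reasons for death".

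Protocol 8.4.3 calls for on-study AEs and SAEs to be tabulated and sets no window.

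**The concern.** In a blinded, placebo-controlled trial, all-cause SAE incidence by arm is the broadest safety comparison that does not depend on an investigator's view of relatedness. Here it ends at day 30, while the sites go on collecting the same events for another 70 days. Drug-related AEs get a 100-day repeat, but drug-related SAEs do not, and the SAP gives no reason for the difference. If non-fatal serious events between days 31 and 100 differed by arm, a reader of the planned tables could not see this for SAEs as a category. The information would have to be rebuilt from the by-subject listing.

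**Working it through.** There is no sample-size or alpha figure to reproduce. The check sets the collection window against the window of each safety summary.

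**1. Which summaries by arm reach day 100**

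| Summary by arm | SAP section | Post-dose window |
|---|---|---|
| SAEs, all-cause and drug-related | 7.6.2 | 30 days |
| AEs leading to discontinuation; to dose delay | 7.6.3; 7.6.4 | 30 days |
| Any AE, non-serious AEs, AEs needing immune-modulating medication | 7.6.5 | 30 days only |
| Select AEs | 7.6.6 | 30 days |
| AEs by subgroup | 7.6.15 | 30 days only |
| Deaths | 7.6.1 | all deaths, 30 and 100 days |
| Drug-related AEs (any grade, 3–4, 5) | 7.6.5 | 30 and 100 days |
| Immune-mediated AEs | 7.6.7 | 100 days |
| Other events of special interest, all-cause and drug-related | 7.6.8 | 100 days |
| Multiple-event tables of all AEs | 7.6.9 | not stated; 7.1.1 allows either |

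**2. Where an SAE on days 31–100 would appear**

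- If fatal: in the 100-day death summary.
- If judged drug-related: in the 100-day drug-related AE table, but not identified as serious.
- If it meets the immune-mediated or special-interest definition: in that table.
- If non-fatal, judged unrelated and outside those groups: in no table by arm with a specified 100-day window.

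In no case does it appear in a table of SAEs as a category.

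**3. Size of the gap in days**

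- Post-dose days not covered: 100 − 30 = 70, which is 70% of the post-dose collection period.
- For a subject who receives all 17 doses (Protocol 4.5), the first eight are two weeks apart, the ninth follows two weeks after the eighth, and the rest are four weeks apart. First to last dose is 8 × 14 + 8 × 28 = 336 days.
- The 30-day window then covers 336 + 30 = 366 of 336 + 100 = 436 days (84%) and leaves out 70/436 = 16%. The share left out is larger for subjects who stop early.

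**4. Are the data there?** Follow-up visit 2 falls 84 ± 7 days after visit 1, which is 30 ± 7 days after last dose (Protocol Table 5.1-3). The nominal time is 30 + 84 = day 114. The range is (30 − 7) + (84 − 7) = 100 to (30 + 7) + (84 + 7) = 128. The in-person schedule therefore spans the whole 100-day period.

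**5. Scale, for illustration only.** The documents give no SAE rate for days 31–100, so p is assumed, equal in both arms. The 760 randomised subjects at 2:1 give about 507 and 253. The 95% half-width for the difference between arms is 1.96 × √[p(1 − p)(1/507 + 1/253)].

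| Assumed p | Subjects added, nivolumab / placebo | Half-width (percentage points) |
|---|---|---|
| 2% | 10 / 5 | 2.1 |
| 5% | 25 / 13 | 3.3 |
| 10% | 51 / 25 | 4.5 |

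**The case against.** **The SAP already looks past day 30 by arm.** A reader might infer that days 31–100 are never compared between arms, or that SAEs in that period appear only in a listing. Neither is so. Deaths, drug-related AEs, immune-mediated AEs (defined regardless of causality in SAP 7.1.1.3) and all-cause events of special interest all reach day 100, and the window for the multiple-event tables is left open. This objection stands, and it narrows the point to SAEs as a category and the remaining non-fatal all-cause AEs.

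**The 30-day window is permitted.** It might be read as contradicting the protocol. It does not: SAP 6.1 lets the window differ by analysis, and Protocol 8.4.3 sets none. This also stands.

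**Late toxicity and understated incidence.** A reader might infer that the plan hides a known late toxicity and so understates SAE incidence. The documents do not say why 100 days was chosen for collection. Protocol 1.4.6 reports, for the earlier multidose study, that most select events came within the first six months of therapy. With no rate for days 31–100, an understatement is possible but cannot be sized.

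**The all-cause comparison becomes harder to read after day 30.** Recurrence requires study drug to stop (Protocol 3.5), and other anticancer therapy is barred only before recurrence (Protocol 3.4.1). Days 31–100 will therefore include events from recurrence and later treatment, possibly more in one arm. Taking all-cause tables to 30 days and drug-related and immune-mediated events to 100 is a coherent choice. This is the strongest objection. It is a good reason to keep the 30-day tables primary, but not to omit a labelled supplement.

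**Some repeats would add little.** AEs leading to discontinuation are defined by the action taken on study drug (SAP 7.1.1), so few should begin after day 30, apart from those during long dose delays. They are left out of the fix.

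**Conclusion.** The point holds as a reporting gap. Both SAE tables and the overall all-cause AE tables end at day 30, while collection of the same events runs to day 100. For the 70 days between, no table is specified that compares SAEs as a category by arm, or that compares non-fatal all-cause AEs outside the drug-related, immune-mediated and special-interest groups.

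The 70% figure describes post-dose days only. It should not be read as 70% of SAE follow-up: for a subject completing treatment on schedule, the uncovered part is about 16% of the period from first dose to day 100.

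The conclusion rests on the SAP text as it stands and on reading the unstated window in SAP 7.6.9 as unspecified. If 7.6.9 were run at 100 days, it would give exposure-adjusted occurrence rates for all AEs over the full period, but still no table of SAEs as a category. The change is a cheap improvement, and the plan is not in error without it.

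**What to change.** - In SAP 7.6.2, repeat the all-cause and drug-related SAE tables with the 100-day window, as supplementary tables.
- In SAP 7.6.5, do the same for the any-AE table by worst grade.
- Keep the 30-day versions as the primary tables.
- In SAP 7.6.9, state which window applies to the multiple-event tables and use the matching exposure definition from SAP 7.1.1.
- Footnote the 100-day all-cause tables to say that they include some events after recurrence or the start of subsequent anticancer therapy, and that this may differ by arm.

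The cost is three repeated tables and one clarifying sentence. The data are already required by the protocol, and no visit, sample size or alpha changes. The downside is the mixing of post-recurrence events, which the footnote and the supplementary status address.

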7.6.3 Adverse Events Leading to Discontinuation of Study Therapy

AEs leading to discontinuation will be summarized by treatment group:

- Overall summary of AEs leading to discontinuation by worst CTC grade (any grade, grade 3-4, grade 5) presented by SOC/PT.
- Overall summary of drug-related AEs leading to discontinuation by worst CTC grade (any grade, grade 3-4, grade 5) presented by SOC/PT.

The analyses will be conducted using the 30-day safety window.

A by-subject AEs leading to discontinuation listing will be provided.

7.6.4 Adverse Events Leading to Dose Modification

AEs leading to dose delay will be summarized by treatment group:

- Overall summary of AEs leading to dose delay/reduction by worst CTC grade (any grade, grade 3-4, grade 5) presented by SOC/PT.

The analysis will be conducted using the 30-day safety window.

A by-subject AEs leading to dose delay/reduction listing will be provided.

7.6.5 Adverse Events

Adverse events will be summarized by treatment group.

The following analyses will be conducted using the 30 days safety window only:

- Overall summary of any AEs by worst CTC grade (1, 2, 3, 4, 5, not reported, total) presented by SOC/PT.
- Overall summary of any AEs presented by worst CTC grade (any grade, grade 3-4, grade 5) by SOC/PT. This table will be restricted to events with an incidence greater or equal to 5% in any treatment group.
- Overall summary of any non-serious AEs presented by SOC/PT. This table will be restricted to events with an incidence greater or equal to 5% in any treatment group.
- Overall summary of any AEs that required immune modulating medication by worst CTC grade (any grade, grade 3-4, grade 5) presented by SOC/PT.
- Overall summary of drug-related AEs by worst CTC grade (1, 2, 3, 4, 5, not reported, total) presented by SOC/PT.

The following analyses will be conducted using the 30 days safety window and repeated using the 100 days safety window:

- Overall summary of drug-related AEs by worst CTC grade (any grade, grade 3-4, grade 5) presented by SOC/PT.

A by-subject AE listing will be provided. A by-subject listing of any AE requiring immune modulating medications will also be provided.

7.6.6 Select Adverse Events (EU/ROW Submissions)

Unless otherwise specified, analyses will be performed by select AE category. Analyses will also be repeated by subcategory of endocrine events.

7.6.6.1 Incidence of Select AE

Select AEs will be summarized by treatment group for each category/subcategory.

The following analyses will be conducted using the 30-day safety window only:

- Overall summaries of any select AEs by worst CTC grade (any grade, grade 3-4, grade 5) presented by Category or Subcategory/PT.
- Overall summaries of any drug-related select AEs by worst CTC grade (any grade, grade 3-4, grade 5) presented by Category or Subcategory/PT.
- Overall summaries of any serious select AEs by worst CTC grade (any grade, grade 3-4, grade 5) presented by Category or Subcategory /PT.
- Overall summaries of drug-related serious select AEs by worst CTC grade (any grade, grade 3-4, grade 5) presented by Category or Subcategory /PT.
- Overall summaries of any select AEs leading to discontinuation by worst CTC grade (any grade, grade 3-4, grade 5) presented by Category or Subcategory /PT.

- Overall summaries of drug-related select AEs leading to discontinuation by worst CTC grade (any grade, grade 3-4, grade 5) presented by Category or Subcategory /PT.
- Summary of frequency of unique select AEs by Category.

A by-subject select AE listing will be provided.

7.6.6.2 Time-to Onset of Select AE

Time-to onset of drug-related select AEs (any grade, grade 3-5) will be summarized for each category/subcategory by treatment group.

Time-to onset analyses are restricted to treated subjects who experienced at least one drug-related select AE in the category/subcategory. The analyses will be conducted using the 30-day safety window.

Additional details regarding the time-to onset definition are described in time-to onset definition subsection of [APPENDIX 1](#).

7.6.6.3 Time-to Resolution of Select AE

Time-to resolution of the following specific events will be summarized separately for each category/subcategory.

- Time-to resolution of drug-related select AE (any grade, grade 3-5) by treatment group
- Time-to resolution of drug-related select AE (any grade, grade 3-5) where immune modulating medication was initiated, by treatment group

Time-to resolution analyses are restricted to treated subjects who experienced the specific events. Time-to resolution where immune modulating medication was initiated analyses are restricted to treated subjects who experienced the specific events and who received immune modulating medication during the longest select AE.

The analyses will be conducted using the 30-day safety window.

The following summary statistics will be reported: percentage of subjects with resolution of the longest select AE, median time-to resolution along with 95% CI (derived from Kaplan-Meier estimation) and ranges.

See time-to resolution definition subsection of [APPENDIX 1](#) for additional details.

7.6.7 Immune-Mediated Adverse Events (US Submission)

IMAEs will be summarized by treatment group for each immune-mediated category / PT using the 100-day safety window:

- Overall summary of non-endocrine IMAEs by worst CTC grade (any grade, grade 3-4, grade 5) where immune modulating medication was initiated presented by Category / PT.
- Overall summary of endocrine IMAEs by worst CTC grade (any grade, grade 3-4, grade 5) presented by Category / PT.
- Overall summary of non-endocrine IMAEs leading to discontinuation by worst CTC grade (any grade, grade 3-4, grade 5) where immune modulating medication was initiated presented by Category / PT.

- Overall summary of endocrine IMAEs leading to discontinuation by worst CTC grade (any grade, grade 3-4, grade 5) presented by Category / PT.
- Overall summary of non-endocrine IMAEs leading to dose delay or reduction by worst CTC grade (any grade, grade 3-4, grade 5) where immune modulating medication was initiated presented by Category / PT
- Overall summary of endocrine IMAEs leading to dose delay or reduction by worst CTC grade (any grade, grade 3-4, grade 5) presented by Category / PT.
- Summaries of time-to onset and time-to resolution of non-endocrine IMAEs where immune modulating medication was initiated presented by Category.
- Summaries of time-to onset and time-to resolution of endocrine IMAEs presented by Category.

A by-subject listing of IMAEs will be provided. By-subject listings of time-to resolution for longest IMAEs cluster (any grade and grade 3-5 in separate summaries) will also be provided. For new studies which collect investigator assessment of potential IMAE data, a by-subject listing of AEs considered as immune-mediated events per investigator but not qualified for IMAEs definition will also be provided.

In addition, for all treated subjects who experienced at least one IMAE, the following data presentation will be provided:

- Summary of subjects who were re-challenged with nivolumab by IMAE category, with extended follow-up

For these, re-challenge is considered to have occurred when last nivolumab infusion was administered after the onset of an IMAE.

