For Cycles 1-8, subjects may have study drug administered up to 2 days before or 3 days after the scheduled dosing date. Subjects may be dosed no less than 12 days from the previous dose. For Cycles 9-17, subjects may be dosed within a +/- 3 day window. A maximum delay of 6 weeks (42 days) between doses of nivolumab (or placebo) during Cycles 1-8 or a maximum delay of 10 weeks (70 days) between doses of nivolumab (or placebo) during Cycles 9-17 are allowed.

4.5.1 *Antiemetic Premedications*

Antiemetic premedications should not be routinely administered prior to dosing of drugs. See [Section 4.5.6](#) for premedication recommendations following a nivolumab related infusion reaction.

4.5.2 *Dose Delay Criteria*

Dose delay criteria apply for all drug-related adverse events. Treatment delays up to 6 weeks (42 days) from the last dose of nivolumab (or placebo) during Cycles 1-8 or up to 10 weeks (70 days) from the last dose of nivolumab (or placebo) during Cycles 9-17 are allowed.

Nivolumab (or placebo) administration should be delayed for the following:

- Any Grade \geq 2 non-skin, drug-related adverse event, with the following exceptions:
 - Grade 2 drug-related fatigue does not require a treatment delay
- Grade 2 drug-related creatinine, AST, ALT or Total Bilirubin abnormalities
- Any Grade 3 skin, drug-related adverse event
- Any Grade 3 drug-related laboratory abnormality (excluding AST, ALT or Total Bilirubin), with the following exceptions for lymphopenia, and asymptomatic amylase or lipase:
 - Grade 3 lymphopenia does not require dose delay
 - Any Grade \geq 3 drug-related amylase or lipase abnormalities that is not associated with symptoms or clinical manifestations of pancreatitis do not require a dose delay.
- Any adverse event, laboratory abnormality, or intercurrent illness which, in the judgment of the investigator, warrants delaying the dose of study medication.

Subjects who require delay of nivolumab should be re-evaluated weekly or more frequently if clinically indicated and resume nivolumab dosing when re-treatment criteria are met.

Note: per BMS standards, the term “interruption” is reserved for interruption of the actual IV infusion during administration. The terms omission and interruption should not be used synonymously when completing the CRF forms.

4.5.2.1 *Adverse Event Management Algorithms for Immuno-Oncology Agents*

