4.5.4 Criteria to Resume Treatment

All criteria to resume treatment apply to both arms given the blinded nature of this study. Subjects may resume treatment with study drug when the treatment-related AE(s) resolve to Grade ≤ 1 or baseline value, with the following exceptions:

- Subjects may resume treatment in the presence of Grade 2 fatigue
- Subjects who have not experienced a Grade 3 drug-related skin AE may resume treatment in the presence of Grade 2 skin toxicity
- For subjects with Grade 2 AST, ALT, or TBILI elevations, dosing may resume when laboratory values return to baseline and management with corticosteroids, if needed, is complete
- Subjects with combined Grade 2 AST/ALT AND total bilirubin values meeting discontinuation parameters ([Section 4.5.5](#)) should have treatment permanently discontinued
- Drug-related pulmonary toxicity, diarrhea, or colitis, must have resolved to baseline before treatment is resumed. Subjects with persistent Grade 1 pneumonitis after completion of a steroid taper over at least 1 month may be eligible for retreatment if discussed with and approved by the BMS Medical Monitor
- Grade 2 or 3 drug-related endocrinopathies adequately controlled with only physiologic hormone replacement may resume treatment after consultation with the BMS Medical Monitor, except for Grade 3 adrenal insufficiency which requires permanent discontinuation as described in [Section 4.5.5](#)

If the criteria to resume treatment are met, the subject should restart treatment at the next scheduled time point per protocol.

However, if the treatment is withheld past the window period of the next scheduled time point per protocol to ensure adequate recovery from the adverse event or tapering of immunosuppression, the dosing should start as soon as possible once it is safe to do so (ie, no need to wait until the

subsequent scheduled time point to resume dosing). If treatment is delayed > 6 weeks (42 days) from the last dose of nivolumab (or placebo) during Cycles 1-8 or > 10 weeks (70 days) from the last dose of nivolumab (or placebo) during Cycles 9-17, the subject must be permanently discontinued from study therapy, except as specified in Section 4.5.5.

4.5.5 Discontinuation of Subjects from Treatment:

All discontinuation criteria for nivolumab also apply for the placebo, given the blinded nature of this study.

Treatment should be permanently discontinued for the following:

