7.1.1.3 Immune-Mediated Adverse Events (US Submission)

In order to further characterize AEs of special clinical interest, analysis of immune-mediated AEs (IMAE) will be conducted. IMAEs are specific events (or groups of PTs describing specific events) that include pneumonitis, diarrhea/colitis, hepatitis, nephritis/renal dysfunction, rash, endocrine (adrenal insufficiency, hypothyroidism/thyroiditis, hypothyroidism, thyroiditis, hyperthyroidism, diabetes mellitus, and hypophysitis), and other specific events, considered as potential immune-mediated events by investigator that meet the definition summarized below:

- those occurring within 100 days of the last dose,
- regardless of causality,
- treated with immune-modulating medication (of note, endocrine AEs such as adrenal insufficiency, hypothyroidism/thyroiditis, hypothyroidism, thyroiditis, hyperthyroidism, diabetes mellitus, and hypophysitis are considered IMAEs regardless of immune-modulating medication use, since endocrine drug reactions are often managed without immune-modulating medication).
- with no clear alternate etiology based on investigator assessment, or with an immune-mediated component

The list of MedDRA preferred terms used to identify IMAEs is revisited quarterly and updated accordingly. The preferred terms used for the selection at the time of the database lock by categories will be provided.

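### The SAP's re-challenge rule requires no hold, so subjects dosed straight through an immune-mediated event are counted with those who stopped and restarted

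*SAP*

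**What the plan says.** SAP 7.6.7 promises a "Summary of subjects who were re-challenged with nivolumab by IMAE category, with extended follow-up". The population is set by the lead-in: "for all treated subjects who experienced at least one IMAE, the following data presentation will be provided". The operational rule follows: "re-challenge is considered to have occurred when last nivolumab infusion was administered after the onset of an IMAE". No grade, action-taken, delay or recovery condition is attached, and no readable part of either document adds one.

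SAP 7.1.1.3 defines IMAEs broadly. They count "regardless of causality" up to 100 days after the last dose. Non-endocrine events must have been treated with immune-modulating medication, but endocrine events "are considered IMAEs regardless of immune-modulating medication use".

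Protocol 4.5.2 lists when dosing should be delayed. For non-skin events the entry starts at Grade "2 non-skin, drug-related adverse event, with the following exceptions". For skin events it is "Any Grade 3 skin, drug-related adverse event". Certain laboratory abnormalities and the investigator's judgment complete the list. Protocol 4.5.4 treats resumption as a separate step: "Subjects may resume treatment with study drug when the treatment-related AE(s) resolve to Grade" 1 or lower, or to baseline, with listed exceptions.

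**The concern.** In ordinary use, re-challenge means giving a drug again after it was withheld. The protocol's background safety summary (Protocol 1.4.6) follows that pattern: of 52 patients managed with immunosuppression in an earlier nivolumab study, 21 are reported as resuming after toxicity resolved, and the others as discontinuing. A reader of a re-challenge table will expect that kind of subject.

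The SAP rule asks only whether the last infusion is later than IMAE onset. It cannot separate a subject who was never stopped from one who was stopped and restarted. It also captures a subject infused once after onset, perhaps before the event was recognised, and then stopped for good. The table is intended for a US submission and is laid out by IMAE category, so the count in each row would not mean what its label says.

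**Working it through.** The plan states no figure on this point, so there is nothing to reproduce. The check is of the rule's logic against the dosing schedule and the delay criteria.

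1. **Can an IMAE occur without a hold?** Set SAP 7.1.1.3 beside Protocol 4.5.2:
   - Grade 1 hypothyroidism is an IMAE category event with or without immune-modulating medication, and it lies below the Grade 2 non-skin trigger.
   - Grade 1 or 2 rash treated with immune-modulating medication can be an IMAE, and it lies below the Grade 3 skin trigger.
   - An event judged not drug-related can be an IMAE, while the listed grade triggers concern drug-related events.

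   In each case a delay is left to investigator judgment, so uninterrupted dosing is compatible with the protocol.

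2. **When does the rule label a never-delayed subject?** Inputs are from Protocol 4.5: 8 doses every 2 weeks, then Cycles 9-17 every 4 weeks.
   - Dose days 1 to 8: 1 + 14 × (0 to 7) = 1, 15, ..., 99.
   - Dose days 9 to 17: 113 + 28 × (0 to 8) = 113, 141, ..., 337.
   - Any onset on days 1 to 336 precedes the last dose and triggers the label.
   - The IMAE window closes at day 337 + 100 = 437.
   - Share of the window by calendar days: 336/437 = 77%.

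   This is a share of time for a full-course subject. It is not an event probability, because the documents give no onset distribution.

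3. **SAP rule against a rule that needs a hold.** Take onset on day 60, between the planned doses on days 57 and 71. Call dosing held if the interval spanning onset exceeds plan by more than 3 days, the threshold in SAP 7.4.2.1.
   - *Never held:* the interval is 71 − 57 = 14 days, so the delay is 14 − 14 = 0. The last dose is day 337 > 60. SAP rule: re-challenged. Hold rule: no.
   - *Held 21 days, then resumed:* the next dose is day 92. The interval is 92 − 57 = 35 days, so the delay is 35 − 14 = 21 > 3. The last dose is 337 + 21 = 358 > 60. Both rules: re-challenged.
   - *Stopped at onset:* the last dose is day 57 < 60. Neither rule: re-challenged.
   - *Dosed on day 71, then stopped:* the delay is 0 and the last dose is day 71 > 60. SAP rule: re-challenged. Hold rule: no.

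4. **Form of the inflation.** Within a category, let R be subjects held and restarted, and C those infused after onset without a hold. The SAP rule reports R + C. The excess is C, a factor of 1 + C/R. The documents give neither R nor C, so no value can be put on this.

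5. **Two further gaps in the same sentence.** The rule refers to any IMAE while the table is by category, and it does not say that the infusion must follow onset in that same category. An infusion on the day of onset is not addressed.

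**The case against.** The strongest reply is that the rule is stated openly, so a reader knows what is counted, and that the protocol speaks of resuming or retreating and gives no rival definition of re-challenge. SAP section 9 says that the plan incorporates an immuno-oncology core SAP, so the rule may be a programme convention; that document is not available to check. SAP 7.6.7 also tabulates IMAEs leading to delay and to discontinuation, and time to resolution. SAP 7.4.1 and 7.4.2.1 provide dosing listings and delay reasons. This material limits the harm, but none of it cross-classifies re-challenged subjects by whether they were held, so the misclassification in the table remains.

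The table's structure also confines the problem, and this part of the reply stands. Non-endocrine IMAEs need immune-modulating treatment, and most drug-related non-skin events from Grade 2 call for a delay. Never-held subjects should therefore fall mainly in the endocrine and rash rows. If infusion is matched to onset within category, unheld endocrine events do not enter the pneumonitis, colitis or hepatitis rows.

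A reader might go further and infer that the table will make restarting nivolumab look safer than it is. The documents do not support that. The readable SAP does not say that the table reports recurrence or worsening. The added subjects also differ in kind: those dosed through mild events could make outcomes look better, while those dosed once and then stopped for good could make them look worse. A reader might also infer that nearly every early IMAE qualifies, or attach a percentage to the inflation. Neither the IMAE rate nor the share dosed through is given, so any such figure would be invented.

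**Conclusion.** The concern holds for the count. As written, the rule classes uninterrupted treatment as re-challenge, and the protocol's own delay criteria make uninterrupted treatment after some IMAEs an expected course. The re-challenge count is inflated whenever at least one such subject exists, chiefly in the endocrine and rash categories. The amount cannot be computed, and the direction of any effect on outcomes after re-challenge is not established.

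This rests on two assumptions: that no unreadable text narrows the rule, and that some subjects with low-grade or non-drug-related IMAEs were dosed on schedule. The consequence is limited to one descriptive safety table. It is worth correcting because a stated rule gives a mislabelled safety count and the remedy is inexpensive.

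**What to change.** Revise the definition in SAP 7.6.7. For each IMAE category, count as re-challenged only subjects with at least one infusion after a dose delay attributed to an IMAE in that category. Attribution can come from the action-taken field recording a delay (SAP 7.1.1), or from a delay of more than 3 days after onset with the IMAE as the recorded reason (SAP 7.4.2.1). Show two further rows: continued without a hold, and not re-dosed after onset. State how a same-day infusion is handled, and in which row a subject dosed after onset and then stopped for good belongs.

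Do not make resolution a condition for re-challenge. Protocol 4.5.4 lets some subjects resume without it, for example with an endocrinopathy controlled by hormone replacement or, in some cases, with Grade 2 skin toxicity. A resolution condition would drop these genuine restarts. Report resolution status at re-dosing as a separate flag.

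At minimum, retitle the table as subjects who received nivolumab after IMAE onset, and split it by whether dosing was held.

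The cost is a few lines of SAP text and a small programming change, using action taken, dosing dates, delay reasons and IMAE onset and resolution dates that the SAP already uses. If the recorded delay reason cannot be tied to a particular IMAE, attribution would rest on the action-taken field alone. The change concerns the analysis definition only, not the clinical rules for holding or resuming treatment.
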